5.5.2.1.1 Sensitivity Analysis of Missing Data

Missing data in this trial could potentially arise from the mechanism of MNAR. Hence, a sensitivity analysis is required to assess the potential impact that missing data under the mechanism of MNAR may have on the estimated results for the primary endpoint.

To facilitate multiple imputation techniques for missing data due to patients who withdraw from the treatment period, it is necessary to divide the treatment period into smaller periods for which missing seizure data can be imputed. Hence, sensitivity analysis of the primary endpoint will be carried out based on periods corresponding to each 14 days of the

treatment period, by multiple imputations on the average daily TSC-associated seizure frequency. The final period will consist of 15 days to include Day 113, where applicable. Following imputation, the imputed periods will be recombined for each patient in order to repeat the primary analysis.

For each 14 calendar days of the treatment period (15 days for the final period), the average daily TSC-associated seizure frequency will be calculated as:

$$(\text{Number of TSC-associated seizures in the period} \div \text{Number of reported days in IVRS in the period})$$

For patients with <6 days in a period, the frequency will be set to missing and will be imputed as part of this analysis.

For intermittent missing data, in which subjects have missing values for intermediate periods but have available data at subsequent periods, imputation will be based on the MCMC methodology. Assumptions underlying this partial imputation step are that patients will follow a similar outcome trajectory as patients in their respective treatment arm that have complete data. Intermittent missing values will be imputed using the MCMC method in PROC MI with an IMPUTE=MONOTONE statement for 200 times for each treatment arm separately. To avoid negative results, a minimum of 0 will be specified in the PROC MI statement. As a result, missing intermediate visits will be imputed and the resulting 200 partially imputed datasets will have a monotone missing pattern.

The remaining monotone missing data will then be imputed using predictive mean matching in which missing observations are imputed with an observed value from another patient whose predicated value is close to the predicated value of the patient with the missing observation. The predictive mean matching is performed using the steps below, in which imputation will be carried out on each of the 200 imputed datasets using the SAS MI procedure (with the 200 imputed datasets included in the 'BY' statement of the MI procedure):

Step 1 – Missing at random (MAR) based multiple imputation for the placebo arm:

- Monotone missing data under the MAR assumption at period t will be imputed using predictive mean matching method from the observed daily TSC-associated seizure frequency at baseline and at each period up to period t (in chronological order)
- The imputation will be realized using the MI procedure with the 'MONOTONE REGPMM' option.
- The imputation model will include baseline daily TSC-associated seizure frequency and each period up to period t (in chronological order).

Step 2 – MNAR based multiple imputation for the GWP42003-P arms (MNAR is assumed for missing values resulting from discontinuation due to any reason or any other monotone missing data):

- With the data imputed from Step 1, monotone missing data under the MNAR at period t will be imputed using predictive mean matching method.
- At each period t, the input dataset for the MI procedure will include all placebo patients and those patients from each GWP42003-P arm (implemented separately by arm) that have values at that period.
- The imputation will be realized using the MI procedure with the 'MONOTONE REGPMM' option.

- The imputation model will include daily TSC-associated seizure frequency at baseline and each period up to period t (in chronological order).

Once all missing values at all periods have been imputed, the TSC-associated seizure count for each period will be calculated as:

(Daily frequency for the period \times Number of days in the period for the non-imputed period or 14 for an imputed period), rounded to the nearest whole number

The result will be 200 fully imputed datasets ready to be analyzed using the same analysis method as the primary endpoint, producing 200 analysis results.

The estimated ratio, 95% CI and p-value from analyses of the 200 imputed datasets will be combined using PROC MIANALYZE.

To test the robustness of the analysis to the MNAR imputations a tipping point analysis will be performed. This will be conducted by adding or subtracting a sensitivity parameter, $k \times$ standard error of the observed average daily TSC-associated seizure frequency in the placebo arm at each period, to the MNAR imputations only at the corresponding period (where $k = 0, \pm 0.5, \pm 1.0, \pm 1.5$, etc.).

The tipping point analysis will be used to explore the robustness of the estimated treatment difference to the degree of decrease or increase (positive values of k represent decrease and negative values represent increase) in MNAR efficacy from the placebo patients.

The increment in the positive value of k will stop once the overall p-value is greater than 0.05. The decrease in the negative values of k will continue until the overall p-value becomes smaller than the p-value from the primary efficacy analysis, for the corresponding Dose Level.

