imputation model will include baseline seizure frequency and each 14-day time-point up to time-point t (in chronological order). With the data imputed from above, monotone missing data of patients in the GWP42003-P groups under the MNAR assumption will be imputed. At each 14-day time-point t, the input dataset for the MI procedure will include all placebo patients and those patients from the GWP42003-P groups that have values missing under MNAR at that time-point. The imputation model will include seizure frequency at baseline and each 14-day time-point up to time-point t (in chronological order) and will be performed for each GWP42003-P group separately.

Full details for this sensitivity analysis will be provided in the SAP.

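### Step 2 of the SAP's MNAR imputation admits active-arm patients with observed rather than missing values, so the analysis and its tipping point cannot be produced as written

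*SAP*

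**What the plan says.** Protocol 13.6.2.1 describes a multiple-imputation analysis in which missing active-arm values are imputed from a model fitted to placebo. At each time-point the input dataset "will include all placebo patients and those patients from the GWP42003-P groups that have values missing under MNAR at that time-point", handled separately for each active group. The protocol then adds: "Full details for this sensitivity analysis will be provided in the SAP".

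SAP 5.5.2.1.1 works in two steps after intermittent gaps have been filled. Step 1 completes the placebo arm under MAR. Step 2 addresses monotone missing data in the active arms, using predictive mean matching. Its heading and first bullet say that missing active-arm values are to be imputed. Its input bullet, however, takes all placebo patients and "those patients from each GWP42003-P arm (implemented separately by arm) that have values at that period".

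The section then states what must come out: "The result will be 200 fully imputed datasets ready to be analyzed using the same analysis method as the primary endpoint". The tipping-point analysis adds or subtracts k standard errors to the MNAR imputations alone, and describes k as a change "in MNAR efficacy from the placebo patients".

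On day counts, the section says "The final period will consist of 15 days to include Day 113, where applicable", but the rule for turning frequencies back into counts uses "Number of days in the period for the non-imputed period or 14 for an imputed period".

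**The concern.** The two documents define opposite sets of active-arm patients for the same step, and the SAP's version conflicts with the purpose of its own Step 2. Among the sensitivity analyses listed for the primary endpoint, this is the only one that imputes data lost through withdrawal under MNAR; the worst-case carry-forward analysis deals with intermittent unreported days. The tipping-point analysis is built on it.

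There are two ways to go wrong. Taken literally, the step imputes nothing in the active arms. Repaired by simply adding the missing patients to the sentence as it stands, the step runs cleanly, but observed active patients remain in the regression and in the donor pool. Patients who stopped the drug are then partly imputed as though they were still benefiting, which gives a milder test than the protocol specifies.

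**Working it through.** **1. Literal reading.** After Step 1 every placebo value exists. Step 2 adds only active patients who have a value at period t. The dataset therefore contains no missing value at t, and zero active-arm values are imputed at any withdrawal rate. The documents give no withdrawal rate. With 70 per arm, the 8 periods that follow from Days 1 to 113 (7 × 14 + 15 = 113) and assumed withdrawal of 5, 15 and 25%, a simulated active arm had about 14, 43 and 71 missing period values; none was filled. Under the protocol's rule all were filled (about 14, 42 and 73 in the corresponding runs), with placebo donors only.

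**2. Pooled repair: donor pool.** Active share = observed active ÷ (70 placebo + observed active).

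| Active values missing (assumed) | Active share of donor pool |
|---|---|
| 10% | 63/133 = 47% |
| 20% | 56/126 = 44% |
| 30% | 49/119 = 41% |

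**3. Pooled repair: effect on the estimate.** Inputs from SAP 3.2: mean reduction 15% on placebo and 50% on active, SD 60%, 70 per arm. Assumed: lognormal ratio of treatment to baseline frequency, baseline median 60 per 28 days with log-SD 1.0, period noise 0.35, withdrawal after period 1 to 3, placebo withdrawal 5%, five matching donors, 300 simulated trials per scenario with 5 imputations each. The effect is the exponentiated difference between arms in mean log(treatment rate ÷ baseline rate).

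| Active withdrawal | Own-arm MAR | Placebo donors only | Pooled donors | Shift | Share of MAR-to-placebo gap removed |
|---|---|---|---|---|---|
| 10%, unrelated to response | 0.466 | 0.481 | 0.471 | 0.010 | 0.010/0.015 = 67% |
| 20%, unrelated | 0.468 | 0.500 | 0.480 | 0.020 | 0.020/0.032 = 63% |
| 30%, unrelated | 0.478 | 0.525 | 0.498 | 0.027 | 0.027/0.047 = 57% |
| 10%, poor responders leave more | 0.456 | 0.467 | 0.461 | 0.006 | 0.006/0.011 = 55% |
| 20%, poor responders leave more | 0.455 | 0.481 | 0.468 | 0.013 | 0.013/0.026 = 50% |
| 30%, poor responders leave more | 0.449 | 0.491 | 0.471 | 0.020 | 0.020/0.042 = 48% |

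With equal withdrawal in both arms (10/10% and 20/20%), placebo-only against pooled donors gave 0.482 vs 0.473 and 0.509 vs 0.488 (unrelated), and 0.468 vs 0.461 and 0.491 vs 0.477 (related). Between 41 and 50% of imputed values came from active donors.

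A repeat at 10, 20 and 30% unrelated withdrawal gave 0.478 vs 0.468, 0.503 vs 0.486 and 0.529 vs 0.502. On the ratio of arithmetic means the shifts were 0.011 to 0.028. A separate simulation with less variable data, and withdrawal spread over the whole treatment period, gave 0.591 vs 0.588, 0.602 vs 0.593 and 0.612 vs 0.602 at 5, 15 and 25% withdrawal: shifts of about 0.003 to 0.010 in the same direction, with 48 to 52% active donors.

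**4. Tipping-point anchor.** Mean difference in imputed frequency (pooled minus placebo-only) ÷ placebo standard error per period = −0.08 to −0.29. So k = 0 moves by about 0.1 to 0.3 units, less than one 0.5 step.

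**5. Day count and offset.** An imputed final period counts 14 days instead of 15: 1/113 = 0.9% at most per affected patient. SAP 5.5.2 sets the offset to the log of days with reported seizure data. If that were carried over unchanged, a patient with 28 reported days and six imputed periods (6 × 14 = 84 days) would have 112 days of counts over a 28-day offset, a fourfold inflation (112/28 = 4). The SAP does not say which offset applies to completed counts.

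**The case against.** The strongest reply is that this is an editorial slip whose meaning is easily recovered. The Step 2 heading, its first bullet, the reference to all missing values having been imputed and the tipping-point text all point to the intended reading, and the protocol gives the sentence in full. The literal version would fail at the first program check. The pooled repair appears in neither document. That the change is absent from SAP 5.8 and the amendments table proves little, because that table leaves out minor changes and corrections. The simulations rest on assumed withdrawal and variability, carry no reported Monte Carlo error, and do not use the planned negative binomial mixed model; the direction follows from assuming the drug works. The tipping-point search would absorb most of a shift below one step. Withdrawal is also penalised in the first key secondary endpoint, where responders must not have withdrawn.

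Much of this stands. The intent is recoverable, the sizes are illustrative, and the amendments table does not settle which wording governs. It does not remove the error: Step 2 contradicts itself whichever document governs. Nor can a programmer assume that protocol wording applies in this block. The SAP departs from the protocol here in the number of imputations (200 against 100), the imputation method (predictive mean matching against regression), the analysis model (the primary model against the Wilcoxon test) and the breadth of the MNAR rule, none of them listed as changes.

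**Conclusion.** The concern holds and should be fixed. As written, Step 2 imputes no active-arm value, so the required completed datasets and the MNAR imputations that the tipping point shifts cannot be produced. That follows from the text alone and needs no assumption.

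The size of harm under the pooled repair does rest on assumptions: an effective drug, 10 to 30% active withdrawal early in treatment, and a simplified effect measure. On those terms the rate ratio is 0.006 to 0.027 too favourable to the drug. That is modest in absolute terms, but it removes roughly half to two thirds of the stress the placebo reference is meant to apply in the scenarios where an own-arm reference was computed. The less variable simulation gave smaller shifts in the same direction. The day-count mismatch is minor; the offset needs stating.

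**What to change.** In SAP 5.5.2.1.1 Step 2, restore the protocol's rule: at each period the input is all placebo patients, as completed in Step 1, plus only "those patients from the GWP42003-P groups that have values missing under MNAR at that time-point", run one active arm at a time. Observed active patients should be explicitly excluded from both the regression and the donor pool. In the same section, give one day count for an imputed final period, and set the offset to the log of the days that the completed counts represent.

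The cost is one corrected sentence and one clarifying line before unblinding. Data collection, design and sample size do not change. The sensitivity estimate may come out slightly less favourable than under a pooled repair.

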5.1.3.4 Treatment Period

The treatment period of the double-blind phase is defined as Day 1 to Day 113.

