5.5.2 Primary Efficacy Endpoint

Blinded Phase:

The primary endpoint is the change in number of TSC-associated seizures (see Section 5.1.3.7) during the treatment period (see Section 5.1.3.4) compared to baseline period (see Section 5.1.3.1) in patients taking GWP42003-P compared with placebo.

The primary endpoint will be analyzed using a negative binomial regression model with the total number of TSC-associated seizures during the baseline period and treatment period as the response variables.

A mixed effect model with repeated measures will be performed modelling the observed total number of TSC-associated seizures in the baseline period and treatment period implemented within the framework of general linear models using the negative binomial response distribution. The model will include stratified age group (1–6 years, 7–11 years, 12–17 years and 18–65 years), time, treatment arm and treatment arm by time interaction as fixed effects and patient as a random effect. The log transformed number of days in which seizure data were reported will be included as an offset. The time variable corresponds to an indicator for the baseline period and treatment period.

The GLIMMIX procedure in SAS will be utilized to perform the analysis with the option maxopt=300 applied. If the model fails to converge, then the statement 'nloptions tech=nrrridg;' will be added. If convergence is still not achieved, then 'method=laplace' will be utilized. However, if convergence is still not possible, then the model will be changed to utilize the log normal response distribution (log rate model). If the log rate model is required and there are patients with no seizures during the baseline or treatment period then all patients will have their baseline and treatment period seizure count adjusted by adding a value of 1.

The estimated least squares mean seizure rate for each period and the estimated ratio of least squares means for treatment period to baseline period and 95% confidence intervals (CIs) will be presented for each treatment arm. In addition, the estimated ratio of each GWP42003-P arm to placebo and 95% CIs will be presented along with the p-value testing the null hypothesis that this ratio is 1.

For each ratio and upper and lower bound of the 95% CI, the percentage reduction will also be presented, calculated as:

$$[1 - (X \div Y)] \times 100\%$$

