This analysis will include only patients who have at least 7 days of seizure data within the maintenance period.

- Primary endpoint analysis repeated using the titration period (see Section 5.1.3.5) each 4 weeks of the maintenance period (Week 1 to 4, Week 5 to 8 and Week 9 to 12 of the 12-week maintenance period).

These analyses will include only patients who have at least 7 days of seizure data within each corresponding 4 week period.

- Primary endpoint analysis repeated using the worst case of last observation carried forward (LOCF), next observation carried backward (NOCB) and the mean from the non-missing data for each patient (rounded up to the nearest integer) to impute missing data arising from unreported days in IVRS during the treatment period only (not the baseline period).

Any intermittent missing data for the number of TSC-associated seizures arising from unreported days in IVRS will be imputed using the worst (highest number of seizures) of the following for each patient: LOCF, NOCB and the mean daily number of seizures during the treatment period (rounded up to the nearest integer) based on using non-missing data:

$$\text{Number of seizures} \div \text{Number of reported days in IVRS}$$

- Primary endpoint analysis repeated using multiple imputation (MI) to impute data under the Missing Not at Random (MNAR) assumption (see Section 5.5.2.1.1).

Open-label Extension:

Open-label summaries will be repeated with the inclusion of an LOCF imputation step, which is described in the following steps:

- If a patient has valid data for ≥ 1 consecutive periods from and inclusive of the first period but only missing periods thereafter, then imputation of the missing period(s) will be carried out using the last 12 weeks of valid data (see Section 5.1.3.3).
- If a patient has intermittent missing periods (i.e. ≥ 1 missing period that falls after a populated period 1 and before subsequent populated periods), then the missing period(s) will be imputed with the closest earlier non-missing period of data.
- If the patient has ≥ 1 consecutive periods of missing data from and inclusive of the first period then no imputation will occur and data from the patient will be excluded from any LOCF presentations.

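### In the MNAR imputation and tipping-point analysis, imputed days are put into the seizure count but, on a literal reading of the SAP, not into the exposure offset.

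*SAP*

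**What the plan says.** SAP 5.5.2.1.1 cuts the double-blind treatment period into 14-day periods. On the last one it says: "The final period will consist of 15 days to include Day 113, where applicable". That agrees with SAP 5.1.3.4: "The treatment period of the double-blind phase is defined as Day 1 to Day 113".

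A period can become imputed without formal withdrawal: "For patients with <6 days in a period, the frequency will be set to missing". Once all periods are filled, each period's count is its daily rate times "Number of days in the period for the non-imputed period or 14 for an imputed period", rounded to a whole number. Periods are recombined within patient, and the 200 completed datasets are "ready to be analyzed using the same analysis method as the primary endpoint".

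SAP 5.5.2 defines that method as a negative binomial mixed model and states one offset: "The log transformed number of days in which seizure data were reported will be included as an offset". Neither section gives a different offset for imputed data.

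The tipping-point step shifts the MNAR imputations by k standard errors of the placebo rate. Positive k adds seizures and stops once p exceeds 0.05. For the other side: "The decrease in the negative values of k will continue until the overall p-value becomes smaller than the p-value from the primary efficacy analysis". A minimum of 0 is specified only for the MCMC step that fills intermittent gaps.

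The worst-case IVRS analysis in SAP 5.5.2.1 fills unreported days in the treatment period, but not at baseline, and repeats the primary model. It does not mention the offset either. SAP 5.1.1.1 uses data reported after withdrawal where they exist.

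**The concern.** A count model with an offset estimates events per unit of exposure, so the count and the exposure must cover the same days. Here the count is extended over imputed days, while the only stated exposure is days with a report. An imputed day is not a reported day. A patient who leaves early would carry about 16 weeks of seizures over a few weeks of exposure.

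The gap may have arisen when the method changed. Protocol 13.6.2.1 planned this imputation for a Wilcoxon test on percentage change, which needs no offset, and left full details to the SAP. The SAP moved it to the negative binomial model without restating the exposure, and SAP 5.8 does not list that change.

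This is the SAP's only MNAR and tipping-point test of the primary endpoint. If the exposure is wrong, the k at which significance is lost reflects the exposure error as well as the assumed loss of efficacy. Two programmers could also reach different p-values from the same text.

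**Working it through.** **Layout.** Seven periods of 14 days plus one of 15 give 7 × 14 + 15 = 113 days, which reproduces the SAP's Day 1 to Day 113.

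**Single patient, literal reading.** Assume a constant true daily rate, a report every day up to day R, and none after. Then

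overstatement = days behind the count ÷ days in the offset.

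When the last period is imputed, the count covers 8 × 14 = 112 days. For R at the end of a period:

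| Last reported day R | Calculation | Overstatement |
|---|---|---|
| 14 | 112/14 | 8.0 |
| 28 | 112/28 | 4.0 |
| 42 | 112/42 | 2.67 |
| 56 | 112/56 | 2.0 |
| 84 | 112/84 | 1.33 |
| 98 | 112/98 | 1.14 |

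**With reporting after withdrawal.** Protocol 9.1.1.10 asks withdrawers who taper to keep using the IVRS, and Appendix 4 shows daily calls to day +9. Assume nine further reported days. Withdrawal at Day 28 then gives reports to Day 37. The third period has 9 reported days, so it is not imputed.
- If a non-imputed period counts its calendar days: 112/37 = 3.03.
- If it counts its reported days: (28 + 9 + 5 × 14)/37 = 107/37 = 2.89.

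On the same basis Day 14 gives 4.65 to 4.87 and Day 56 gives 1.65 to 1.72.

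**Active:placebo ratio.** Withdrawal rates are not in the documents, so these are assumptions: last reported day uniform over Days 6 to 98, no later reporting, calendar days in partly observed periods, and averaging on the log scale. The mean of ln(112/R) over R = 6 to 98 is 0.958 (geometric mean 2.61). The bias is exp[(active proportion − placebo proportion) × 0.958]:
- 10% against 3%: exp(0.07 × 0.958) = 1.07
- 15% against 3%: exp(0.12 × 0.958) = 1.12
- 20% against 5%: exp(0.15 × 0.958) = 1.15
- equal proportions and timing: 1.00

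**14 against 15 days.** An imputed last period loses 1/15 = 6.7% of its count. Against a 113-day offset the total is 112/113 = 0.991, a 0.9% understatement. If the offset also used 14, the effect would be nil.

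**Reported or calendar days.** The SAP does not say which applies to a non-imputed period. With calendar days in the count and reported days in the offset, even a completer with 90% reporting is overstated by 1/0.90 = 1.11.

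**Worst-case IVRS imputation.** If unreported days are filled at the patient's own mean and the offset is unchanged, the overstatement is 1/(1 − proportion unreported): 1.05 at an assumed 5% and 1.11 at 10%.

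**Negative k.** The remaining gaps are filled by predictive mean matching, so an imputed value is a donor's value and can be 0. Any negative k then gives a negative rate for that period. Nothing guarantees that the p-value will fall below the primary one.

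**After the fix.** With the offset equal to the days behind the count, the overstatement is 1.00 for every withdrawal day.

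**The case against.** The best counter-argument is that the SAP never says the reported-days offset is kept for imputed data. The count formula itself names the days used, and a programmer could take those as the exposure, in which case nothing is overstated. It stands that the carry-over is the literal reading and not an explicit instruction. But the SAP sends the data to the primary method, and that method has one stated offset.

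Second, the large ratios belong to individual early withdrawers, and the higher ones assume no later reporting. This stands. A reader might infer a several-fold error in the treatment effect; the arm-level calculation does not support that.

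Third, the error would be conservative if withdrawal is commoner on active treatment. That is conditional: more or earlier withdrawal on placebo would reverse it.

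Four other stronger readings also fail:
- That the 14-day rule adds to the overstatement. It acts the other way.
- That the worst-case IVRS analysis also tests informative withdrawal. SAP 5.5.2.1 limits it to intermittent unreported days, and similar reporting across arms would largely cancel its effect in the active:placebo ratio.
- That withdrawal time replaces the missing-data mechanism. Imputed values still come from the placebo-based model and the k shift; the exposure error is added to them.
- That the entry minimum of 8 seizures in 28 days (0.29 per day) shows when a shifted rate turns negative. It is a baseline threshold, imputed values are donors' treatment-period rates, and the standard error is not given. A negative period value also need not make the recombined total negative, and the robustness conclusion comes from positive k.

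**Conclusion.** The point holds for the MNAR multiple-imputation and tipping-point analysis. Followed as written, the stated rules put imputed days in the count and leave them out of the exposure, so this is more than missing detail. The single-patient figures rest on a constant rate and on the literal offset. The shift of about 1.07 to 1.15 in the arm ratio rests on assumed withdrawal patterns; on those assumptions it goes against the active arm and could bring the tipping point to a smaller k. The primary analysis and the testing hierarchy are not affected. The 14-against-15 conflict is a separate and minor contradiction. The open-ended negative-k series is a specification gap on the favourable side of the tipping-point analysis.

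**What to change.** Amend SAP 5.5.2.1 and 5.5.2.1.1 before unblinding:

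- State that for imputed datasets the offset is the log of the total days over which the count was built.
- Use 15 days for an imputed last period.
- Say whether a non-imputed period uses reported or calendar days, and match the offset to that choice.
- Apply the same offset rule to the worst-case IVRS imputation.
- Floor shifted rates at 0 in the tipping-point step, and end the negative-k series at a pre-set k. Once rates sit at the floor, more negative k changes nothing, so a p-value rule alone might never stop.

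The cost is a few sentences and matching code. No data collection or primary result changes.

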3.2 Definition of Sample Size

Blinded Phase:

A total of 210 patients will be enrolled. The 210 patients will be randomly allocated to 1 of 4 treatment arms (GWP42003-P 25 mg/kg/day, GWP42003 P 50 mg/kg/day, placebo 25 mg/kg/day dose volume equivalent, or placebo 50 mg/kg/day dose volume equivalent) at a 2:2:1:1 ratio. The placebo arms will be pooled for the analyses of efficacy.

If it is assumed that patients in the placebo arm will experience a mean reduction in seizure frequency of 15% (from baseline), patients receiving GWP42003-P will experience at least a 50% reduction in seizures and a common standard deviation of 60%, then this sample size of 70 patients per arm will be sufficient to detect a difference in response distributions with 90% power. This test is based on a two-sided non-parametric Mann-Whitney-Wilcoxon test for continuous response data with a 5% significance level.

Open-label Extension:

All patients who wish to continue on IMP following the blinded phase.

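### The tipping-point shift has no floor at zero, which makes the negative-k results for the primary endpoint unreliable

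*SAP*

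**What the plan says.** SAP Section 5.5.2.1.1 imputes average daily TSC-associated seizure frequency in 14-day periods. There are four stages.

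- Intermittent gaps are filled by MCMC. Here the SAP guards against impossible values: "To avoid negative results, a minimum of 0 will be specified in the PROC MI statement".
- The remaining (monotone) gaps are filled by predictive mean matching, which copies an observed value from another patient. Those values cannot be negative, but they can be zero.
- Imputed frequencies are multiplied by 14 and rounded to whole counts. Periods are then recombined per patient and the primary negative binomial analysis (Section 5.5.2) is repeated.
- For the tipping-point analysis, the MNAR imputations (GWP42003-P arms only) are shifted. "This will be conducted by adding or subtracting a sensitivity parameter" is the instruction, and the unit is the "standard error of the observed average daily TSC-associated seizure frequency in the placebo arm at each period". Positive k means less efficacy and runs until p exceeds 0.05. Negative k means more efficacy, with this rule: "The decrease in the negative values of k will continue until the overall p-value becomes smaller than the p-value from the primary efficacy analysis".

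No lower bound is stated for the shifted frequencies or for k.

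**The concern.** With negative k, the same absolute amount is taken off every MNAR-imputed frequency in a period, however low that frequency is. The MCMC minimum acts before the shift and does not constrain it. Neither the conversion to counts nor the recombination truncates. Two things can then go wrong.

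- A negative imputed period is added to the patient's observed periods. If the total stays at or above zero, it is fitted, but with seizures that were really observed cancelled out.
- If the total falls below zero, it lies outside the support of the negative binomial distribution. The patient drops out of the fit, or the fit fails.

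The rule for negative k sets no limit. If the drug works, placebo-based imputation should weaken the effect at k = 0, so the search would be expected to go below zero. At stake is the interpretability of that half of a planned sensitivity analysis of the primary endpoint, for each dose.

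**Working it through.** **Inputs.** 70 patients per arm with placebo pooled (SAP 3.2); 14 days per imputed period, with rounding (SAP 5.5.2.1.1); lowest eligible baseline of 8 seizures in 28 days (protocol criterion 6.1.11), so 8/28 = 0.286 per day. The placebo SD of daily frequency is not given. The 60% in SAP 3.2 is an SD of percentage change and cannot stand in for it, so SDs of 0.5 to 6 per day are assumed.

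**The plan's own figure.** The tipping-point text states none. The 70 per arm reproduces: a difference of 35 points with SD 60 at two-sided 5% needs 62 per arm by the normal formula. Dividing by the Wilcoxon relative efficiency gives 65 (efficiency 0.955) or 72 (worst case 0.864). Power at 70 is 93.2%, 92.1% and 89.4% respectively, consistent with the stated 90%.

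**Where the shift goes negative.** SE = SD/√70. A rate of 0.286 reaches zero at k = -0.286/SE. An imputed zero gives a 14-day count of round(14 × k × SE).

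| Assumed SD | SE per day | k at which 8/28 reaches zero | First half-step below zero | Count from an imputed 0 at k = -0.5 |
|---|---|---|---|---|
| 0.5 | 0.060 | -4.8 | -5.0 | 0 (-0.42 before rounding) |
| 1 | 0.120 | -2.4 | -2.5 | -1 |
| 2 | 0.239 | -1.2 | -1.5 | -2 |
| 4 | 0.478 | -0.6 | -1.0 | -3 |
| 6 | 0.717 | -0.4 | -0.5 | -5 |

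Rounding delays the first negative count by one half-step for SD 0.5 and SD 1.

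**One patient.** Take 8 observed seizures in 28 days, then six periods imputed at 8/28 per day (14 × 8/28 = 4 per period).

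- SD 1, k = -3: 4 - 14 × 3 × 0.120 = -1.0, so -1 per period. Total 8 - 6 = 2; six observed seizures are cancelled.
- SD 2, k = -2 (or SD 4, k = -1): 4 - 6.7 = -2.7, rounded to -3. Total 8 - 18 = -10, which cannot be fitted.
- With a floor at 0, the total is 8 in each case.

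**Effect on the search.** A simulation used 70 placebo and 70 active patients, eight periods, donor imputation from placebo, 10 imputations pooled by Rubin's rules, and a negative binomial regression standing in for the planned mixed model. Negative totals were left out of the fit. Assumed: baseline median 30 or 56 per 28 days, log-scale SD 0.8 to 1.3, and 10% or 20% active-arm drop-out; four scenarios, one run each. Shifted periods were negative in 2% to 50% of cases at k = -0.5, 7% to 76% at k = -1, and none for k ≥ 0. In the scenario with median 56, log-SD 1.0 and 10% drop-out (8 drop-outs, mean SE 1.298 per day, primary p = 3.6e-8):

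| k | p, no floor | p, floor at 0 | Mean negative totals (no floor, of 8) |
|---|---|---|---|
| +2 | 0.059 | 0.059 | 0 |
| 0 | 3.4e-7 | 3.4e-7 | 0 |
| -0.5 | 9.6e-8 | 2.3e-8 | 2.3 |
| -1 | 4.3e-7 | 1.9e-8 | 6.3 |
| -3 | 6.6e-7 | 2.7e-8 | 8.0 |

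Without a floor, p never fell below the primary p-value at any k tried down to -10, so the rule did not end the search. With the floor it was met in all four scenarios, and every k ≥ 0 result was identical with and without the floor.

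**The case against.** The strongest reply is that this is a gap in wording on the side that matters less. The robustness question is how much worse drop-outs must do before significance is lost. That is the positive-k search, which only adds seizures. The SAP's authors plainly meant to avoid negative values, since they say so at the MCMC step, and a programmer may truncate without being told. The search may also stop early: in one simulated scenario p at k = 0 (0.0054) was already below the primary p (0.0063). With a small placebo SD, k would have to go far before an imputed rate of 8 per 28 days turned negative.

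The point about scope stands in full, and the point about size in part. What does not stand is reliance on silent truncation. The written rule is to subtract, convert, round and recombine, and followed as written it can produce inadmissible totals. Two programmers could report different results from the same SAP.

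A reader might also infer that the reported negative k will look closer to zero than it should. The documents do not support a fixed direction. Cancelled seizures push that way, but the patients lost for negative totals are those with the lowest active-arm totals, and losing them tends to weaken the effect, as in the second table.

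**Conclusion.** The point holds for negative k only. As written, the shift can cancel observed seizures and can produce patient totals that the negative binomial cannot fit. The negative-k results would then be unreliable in no fixed direction, and the stopping rule might not be met.

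How soon this happens depends on the placebo standard error, which the documents do not give. The range of about k = -4.8 to -0.4 rests on the assumed SDs and on all 70 placebo patients contributing to each period. The simulation figures are single runs under assumed rates and illustrate size only.

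A reader might infer that the whole tipping-point analysis is compromised, or that negative counts go straight into the model. Neither follows. The positive-k tipping point is untouched, and the model receives patient totals after recombination, not single periods. The primary analysis and the sample size are also unaffected. This is a minor correction, worth making because it is nearly free.

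**What to change.** Add to SAP Section 5.5.2.1.1, after the description of the shift:

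- Any MNAR-imputed daily frequency that is below 0 after the shift is set to 0 before conversion to a count.
- The negative-k search ends when p falls below the primary p-value for that dose, or when all shifted MNAR imputations equal 0, whichever comes first.

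The second condition is needed because, once every shifted imputation is 0, lowering k further changes nothing, so the present stopping rule is not guaranteed to be met even with a floor. The additive parameter can stay as specified. The cost is a sentence or two in the SAP and about one line of code, with no change to any result for k ≥ 0.
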